### **7.2. Primary objective**

To identify any associations between the type and number of doses of antimicrobial drugs administered during the perioperative period and the incidence of surgical site infection within 30 days after surgery.

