#### 4. Summary and Synopsis

Short title	SAPPHIRE study
Methodology	National, multi-centre prospective observational cohort study collecting only anonymised data
Research sites	NHS hospitals undertaking elective surgery as listed above
Objectives	
 
1. To identify association between the use of perioperative antimicrobial drugs and the incidence of postoperative surgical site infection.
 
2. To identify association between the use of perioperative antimicrobial drugs and other perioperative complications.
 
3. To identify association between antimicrobial allergy labels and perioperative complications.
 

Number of participants	13,720 patients data sets
Inclusion criteria	
Adult patients (aged <math>\geq 18</math> years) undergoing one of the following surgical procedures:
 
 
• Primary hip or knee replacement
 
• Internal fixation of a closed long bone fracture (upper or lower limb)
 
• Colorectal resection
 
• Trans-urethral resection of prostate or bladder tumour
 
• Caesarean section
 
• Hysterectomy (vaginal or abdominal)
 

Exclusion criteria	
 
• Use of antibiotics in the two weeks prior to surgery
 
• Previous participation in the study
 

Statistical methodology and analysis	
Continuous variables will be reported as a mean with standard deviation or median with interquartile range. Multivariable regression analysis will be used to test associations between exposure and outcome measures, adjusting for pre-specified covariates that are plausibly associated with both exposure and outcome. Logistic regression models will be used for binary outcomes and linear regression models for continuous outcomes. The threshold for statistical significance will be 5%. A single final analysis is planned at the end of the study.

Study duration	31 months
----------------	-----------

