## **6.2. Rationale**

Our aims of the study are to provide detailed data describing the clinical effectiveness of antimicrobial prophylaxis and define the risks of harm during the perioperative period. This will include:

1. An understanding of the treatment effect of antimicrobial prophylaxis in preventing SSI
2. Description of clinically relevant harm associated with the use of antimicrobial prophylaxis
3. Details of any association between drug allergy labels and SSI

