## **7. Study Objectives**

### **7.1. Exposures of interest**

- Number of doses of antimicrobial drugs administered as prophylaxis before, during or after surgery to prevent an infection
- Label of allergy to any drug

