### **7.3. Primary outcome measure**

The primary outcome is surgical site infection (bacteriuria for urological surgery) within 30 days after surgery (US Centre for Disease Control Criteria).

- Superficial surgical site infection
- Deep surgical site infection
- Organ space surgical site infection
- Urinary tract infection or bacteriuria

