### **7.5. Secondary outcome measures**

- Number of antimicrobials to treat an infection
- Incidence of antimicrobial side effects within 30 days after surgery:
  - Acute kidney injury of any cause
  - Diarrhoeal illness of any cause

- Hearing loss, tinnitus or vertigo of any cause
- Suspected allergic reaction to antimicrobials
- Suspected allergic reaction to any other drug
- Incidence of postoperative infection within 30 days after surgery
- Incidence of all postoperative complications within 30 days after surgery
- Mortality at 30 days

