## **9. Statistical Considerations**

We will use a pre-specified statistical analysis plan. The sample size required to detect an association between SSI and dose was calculated using the 'simsam' package in STATA (Version 17.0), which uses simulation. We assumed that dose was a Poisson random variable with mean and variance 2, and that there was a linear relationship between  $\log(p/(1-p))$  and dose, where  $p$  is the risk of SSI. To specify the association we would like power to detect we specified the SSI risk at the mean dose (10%) and the SSI risk at dose 0 (12%), which then determines the coefficients in the linear relationship between  $\log(p/(1-p))$  and dose. To demonstrate an association between dose and SSI risk using logistic regression, with 90% power at the 5% significance level, we require 6000 patients. Also, to demonstrate an association between allergy label (binary exposure) and complications. The incidence of complications in exposed 15% and unexposed 10%, with 80% power at the 5% significance level we require 1372 patients. However, we expect only 10% of the sample to have an allergy label, so the total sample size would need to be 13720. Considering both sample size calculations for our primary and principal secondary outcomes we aim to recruit a total 13720 patients.

The primary analysis will test associations between antimicrobial prophylaxis and surgical site infection. Secondary analyses will examine the association between the type and number of doses of antimicrobial prophylaxis and potential antibiotic-related harms (including allergic reactions, acute kidney injury, diarrhoeal illness within 30 days after surgery), as well as other postoperative infective complications within 30 days after surgery, and mortality at 30 days. In addition, we will examine any associations between the presence of drug allergy labels and SSI, other postoperative infections and antibiotic-related complications. We will report continuous variables as mean with standard deviation or median with interquartile range. We will use multivariable regression analysis to test associations between exposure and outcome measures, adjusting for pre-specified covariates that are plausibly associated with both exposure and outcome. We will use logistic regression models for binary outcomes and linear regression models for continuous outcomes. The threshold for statistical

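### The primary exposure is worded in two ways and has no end time, so infection can change the dose count it is being related to

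*Protocol*

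**What the plan says.** The exposure appears in four places, in two forms.

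- **Prophylaxis only.** Protocol 7.1 gives "Number of doses of antimicrobial drugs administered as prophylaxis before, during or after surgery to prevent an infection". Section 9 says "The primary analysis will test associations between antimicrobial prophylaxis and surgical site infection".
- **Any perioperative antimicrobial.** Protocol 7.2 sets the primary objective as "To identify any associations between the type and number of doses of antimicrobial drugs administered during the perioperative period" and SSI. Synopsis objective 1 is equally broad: "use of perioperative antimicrobial drugs and the incidence of postoperative surgical site infection".

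The perioperative period is not defined in the glossary or in Appendix A. Protocol 7.1 includes doses after surgery but does not say when counting stops. On the outcome side, 7.3 reads "The primary outcome is surgical site infection (bacteriuria for urological surgery) within 30 days after surgery". Treatment doses have their own place among the secondary outcomes in 7.5: "Number of antimicrobials to treat an infection". The first aim in 6.2 is causal in tone: "An understanding of the treatment effect of antimicrobial prophylaxis in preventing SSI".

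**The concern.** A dose count that is still open after surgery overlaps the time in which SSI can occur. Two mechanisms then run from the outcome back to the exposure.

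- **Upward.** Doses given because infection is suspected or diagnosed are added to the count of patients with SSI. The 7.2 wording admits them directly. Under 7.1 they can still enter if a dose extended on suspicion is recorded as prophylaxis.
- **Downward.** When infection is recognised and the patient moves to treatment, the prophylaxis count stops early. Patients with SSI then show fewer prophylactic doses because they became infected.

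Section 9 plans to adjust for covariates associated with both exposure and outcome. That deals with common causes. It does not remove an effect of the outcome on the exposure. At stake is whether the odds ratio per dose can be read as evidence about prophylaxis, given that the effect the study is designed to find is small.

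**Working it through.** **1. The plan's own figure.** Inputs from section 9: dose is Poisson with mean 2, SSI risk is 10% at the mean dose and 12% at dose 0, power 90%, level 5% (taken as two-sided).

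- Slope = (logit 0.10 − logit 0.12) / 2 = (−2.1972 + 1.9924) / 2 = −0.1024, an odds ratio of 0.903 per dose.
- For a Wald test, N = (1.960 + 1.282)² × v / slope², where v is the slope element of the inverse per-patient information. Here v = 6.02, so N = 10.51 × 6.02 / 0.01049 ≈ 6036.

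This agrees with the stated 6000 (power 89.8%). At 13,720 patients the power is 99.8%. The sample size is not in error.

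**2. Upward mechanism.** Assume that a fraction f of SSI cases has three extra doses counted because of the infection. Fit the logistic model to the resulting expected distribution and take the standard error at N = 13,720. The fraction f and the three doses are assumptions; the protocol gives neither.

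| True OR per dose | f | Fitted OR | Significant, protective | Significant, harmful |
|---|---|---|---|---|
| 1 (risk 10%) | 2% | 1.030 | 0% | 32% |
| 1 | 5% | 1.074 | 0% | 96% |
| 1 | 10% | 1.146 | 0% | 100% |
| 0.903 | 0 | 0.903 | 99.8% | 0% |
| 0.903 | 5% | 0.977 | 21% | 0.1% |
| 0.903 | 10% | 1.050 | 0% | 72% |

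Simulation of the second row gave odds ratios of 1.07 to 1.08 and 94–98% false positives. The planned effect is cancelled (fitted OR = 1) when about 20% of SSI cases have one extra dose counted, 6.5% have three, or 3.3% have six.

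**3. Downward mechanism.** There is no true effect. Planned doses are 8-hourly, the first is always given, and a fraction f of SSIs starts uniformly over days 0–3 and stops the count. With nine 8-hour intervals in 72 hours, the count becomes min(planned, c), with c equally likely to be 1 to 9.

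| f | Fitted OR | Significant in either direction (nominal 5%) |
|---|---|---|
| 5% | 0.994 | 6% |
| 10% | 0.989 | 9% |
| 20% | 0.978 | 20% |
| 30% | 0.967 | 38% |

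Simulations of the last two rows ranged from 18% to 42%; those of the first two ranged from 4% to 9%. The result depends heavily on timing. If affected patients instead lose two doses (never the first), f = 10% gives an OR of 0.954 and f = 20% gives 0.908. That is a severe case, because a later SSI cannot undo doses given before or during surgery.

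**The case against.** The strongest reply is that the protocol already keeps treatment doses out. Section 7.1, which defines the exposure, says prophylaxis; section 9 words the primary analysis the same way; and 7.5 lists treatment antimicrobials as an outcome. On that view 7.2 is loose shorthand. Much of this stands. A reader might infer from 7.2 that the primary analysis will count treatment doses, but the other sections do not support that. What remains is that the primary objective and the synopsis contradict the definition. Sorting doses by intent also does not sort them by time: intent has to be read from the notes, and a switch to treatment still shortens the prophylaxis count.

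A reader might also infer that doses are counted for the whole 30 days. No section says so; the window is unstated.

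A third reply is that a closing rule may be in the statistical analysis plan, which section 9 promises and which is not at hand. That is fair for the landmark and the handling of early events. It does not settle the conflicting wording in the protocol itself, and no analysis plan can use dose times or a day of SSI that were not recorded.

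Finally, the shares in the illustration have no source in the document. That stands in full. The tables show how sensitive the estimate is, not how biased it will be.

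**Conclusion.** The point holds in a limited form. The exposure is defined inconsistently, and the plan as written lets infection alter the dose count in either direction. Because the planned effect is only 0.903 per dose and the sample is large, small amounts of upward contamination matter: three extra doses in 5% of SSI cases would give about 1.07 per dose and a false finding in about 96% of analyses. The downward mechanism matters only if a sizeable share of SSIs starts while prophylaxis is still being given. At 20–30% over days 0–3 it gives about 0.98–0.97 with roughly 20–40% false positives; at 5–10% it is negligible. All of these figures rest on assumed shares, extra doses and timing.

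A reader might conclude that the dose–SSI association will be wholly an artefact. The documents do not show that; it is a possibility under chosen inputs. This should be fixed, but it is not a reason to reject the primary analysis.

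**What to change.** 1. Use the 7.1 prophylaxis wording in 7.2 and in synopsis objective 1.
2. State when the dose count closes. Assign doses given from first suspicion of infection to the existing 7.5 outcome on treatment antimicrobials. This stops the upward mechanism but not the downward one, so item 4 is also needed.
3. Make sure the eCRF records dose times and the day of SSI.
4. Pre-specify an analysis whose exposure is fixed before SSI can occur. Options are doses up to the end of surgery, a landmark (for example 24 h) with SSI counted only after it, or dose as a time-dependent exposure.

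The cost is wording, a little more data entry and one further analysis. The landmark version has a real drawback: it leaves out SSIs before the landmark and prophylactic doses after it, and those later doses are what separate prolonged from short courses, a comparison that the background (6.1) raises. It should therefore be a sensitivity analysis or one option among these, not a required redefinition of the primary analysis.

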### **7.3. Primary outcome measure**

The primary outcome is surgical site infection (bacteriuria for urological surgery) within 30 days after surgery (US Centre for Disease Control Criteria).

- Superficial surgical site infection
- Deep surgical site infection
- Organ space surgical site infection
- Urinary tract infection or bacteriuria

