## 6. Introduction

### 6.1. Background

Surgical site infection (SSI) is an important and preventable cause of postoperative morbidity which affects 250,000 of the five million NHS patients who undergo surgery every year. Patients who develop SSIs stay longer in hospital, have an increased mortality, and can experience poorer quality of life. Treatment of SSIs is also associated with significant healthcare costs to healthcare providers.

Antimicrobial prophylaxis is an important method for preventing SSI and is a widely used practice in surgical care. However, advances in surgical techniques (e.g. laparoscopic and robotic), operative theatre design (e.g. laminar flow air conditioning) and perioperative care (e.g. pre-operative patient showers) have reduced the inherent risk of SSI. The evidence supporting the use of antimicrobial prophylaxis has significant limitations, with many trials conducted more than 20 years ago and potentially less relevant to contemporary practice. We conducted an extensive systematic review and meta-analysis and found that while antimicrobial prophylaxis is associated with a 1% absolute risk reduction for SSI, the evidence quality was poor. In a number of surgical groups, patients receiving prolonged course of prophylaxis experienced a small benefit in terms of infection risk, compared to those receiving short-duration courses (Risk Difference -0.01 [-0.02 to -0.01]; I=52%). A similar result was seen when comparing no prophylaxis to ≥1 dose (Risk Difference -0.02 [-0.03 to -0.02]; I=62%). This suggests that antimicrobial prophylaxis might not be required in the doses currently prescribed or, in some cases, not required at all.

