### **7.7. Inclusion criteria**

Adult patients aged 18 years and over undergoing one of the following surgical procedures:

- Primary hip or knee replacement
- Internal fixation of a closed long bone fracture (upper or lower limb)
- Colorectal resection
- Trans-urethral resection of prostate or bladder tumour
- Caesarean section
- Hysterectomy (vaginal or abdominal)

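### The primary outcome puts bacteriuria together with surgical site infection, but the objective, sample size and primary analysis call the result surgical site infection only

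*Protocol*

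**What the plan says.** Protocol section 7.3 defines a single primary outcome: "The primary outcome is surgical site infection (bacteriuria for urological surgery) within 30 days after surgery". The list beneath it gives superficial, deep and organ-space SSI, and then "Urinary tract infection or bacteriuria". That last item carries no restriction to urological patients, although the sentence above it does.

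The urological operation concerned is one of the six procedure groups in section 7.7: "Trans-urethral resection of prostate or bladder tumour". The Protocol gives no expected case mix.

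Elsewhere only SSI is named. The primary objective (section 7.2) concerns "the incidence of surgical site infection within 30 days after surgery". Section 9 says "The primary analysis will test associations between antimicrobial prophylaxis and surgical site infection". Its sample size uses one risk and one slope for everybody: "we specified the SSI risk at the mean dose (10%) and the SSI risk at dose 0 (12"%). Models are to be fitted "adjusting for pre-specified covariates that are plausibly associated with both exposure and outcome", with the covariates not named. The secondary outcomes in section 7.5 include all postoperative infection, but neither SSI alone nor bacteriuria alone.

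**The concern.** Incisional infection and a urinary finding after transurethral resection are different events. They may have different base rates and may respond differently to prophylaxis. Section 6.2 gives the study's first aim as the effect of prophylaxis in preventing SSI. If the model estimates one dose coefficient across all patients, the figure reported as the SSI association is a weighted average of an SSI association and a bacteriuria association.

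Adjusting for procedure does not solve this. Separate intercepts absorb the difference in base rates, but the dose slope is still shared. Below a risk of 50%, a group with a higher event risk also carries more weight per patient. Two errors follow: bacteriuria alone could produce a significant result labelled SSI, or a null in urology could dilute a real SSI effect.

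The unrestricted fourth item widens the gap. Read literally, a urinary tract infection after a caesarean section or a hip replacement would also count as a primary event.

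**Working it through.** **Inputs from the Protocol (section 9 unless stated).** Dose is Poisson with mean 2. SSI risk is 10% at the mean dose and 12% at dose 0. The test is at 5% (taken as two-sided). The primary calculation gives 6000 patients, and the planned total is 13,720. Section 6.1 says that SSI "affects 250,000 of the five million NHS patients who undergo surgery every year", which is 5%.

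**Inputs assumed, because the Protocol gives none.** Urological share f of 10% or 1/6; bacteriuria risk 10% to 35%; SSI risk in the other procedures 5% (the section 6.1 figure) to 10% (the planning figure); bacteriuria odds ratio (OR) per dose of 0.903 (the planned value) or 0.80 (illustrative only).

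**Step 1: the plan's own figure.** Slope b = [ln(0.10/0.90) − ln(0.12/0.88)]/2 = (−2.1972 + 1.9924)/2 = −0.1024, so OR = 0.903 per dose. The information per patient over Poisson(2) doses is 0.166. N = [(1.960 + 1.282)/0.1024]²/0.166 ≈ 6036. Simulated power at 6000 is 90.4%. The stated 6000 is reproduced, using one slope for all patients.

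**Step 2: what a pooled slope estimates.** With separate intercepts for urology (u) and the rest (s), approximately:

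- w_u = f × 2 × p_u(1 − p_u) and w_s = (1 − f) × 2 × p_s(1 − p_s), where 2 is the dose variance
- pooled slope = (w_u b_u + w_s b_s)/(w_u + w_s)
- SE = 1/√[13,720 (w_u + w_s)]
- P(significant) = Φ(|z| − 1.96) + Φ(−|z| − 1.96)

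**Step 3: no SSI effect, bacteriuria at the planned slope.**

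- Upper end (f = 1/6, bacteriuria 35%, SSI 5%): w_u = 0.0758, w_s = 0.0792, urological weight 0.489. Pooled slope = −0.0501 (OR 0.951), SE = 0.0217, z = 2.31, giving 64%. The full large-sample logistic fit gives 62%.
- Lower end (f = 10%, both risks 10%): weight 0.10, slope −0.0102 (OR 0.990), SE 0.0201, z = 0.51, giving 8%. The full fit also gives 8%.

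Full fit at f = 1/6, probability of a significant pooled result:

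| Bacteriuria risk | SSI 5% | SSI 10% |
|---|---|---|
| 35% | 62% | 47% |
| 20% | 40% | 28% |
| 10% | 18% | 13% |

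The pooled OR lies between 0.95 and 0.99 throughout.

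**Step 4: no SSI effect, bacteriuria OR 0.80.** With f = 1/6, the full fit gives about 81% (bacteriuria 20%, SSI 10%, pooled OR 0.95) to 99.7% (bacteriuria 35%, SSI 5%, pooled OR 0.90). The assumed risks are averages over doses here; fixing them at the mean dose moves these figures by about a percentage point or less.

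**Step 5: planned slope for SSI, none for bacteriuria (f = 1/6, SSI 5%).**

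- Bacteriuria 20%: SSI weight 0.598, slope −0.0612, SE 0.0235, z = 2.61, giving 74% (full fit 70%, pooled OR 0.94).
- Bacteriuria 35%: slope −0.0523, z = 2.41, giving 67% (full fit 63%, pooled OR 0.95).
- At 10% SSI the loss is small. With bacteriuria 35%, w_s = 0.150, SSI weight 0.664, slope −0.0680, SE 0.0180, z = 3.79, giving 97% (full fit 95%).

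**Step 6: power of separate estimates at f = 1/6, planned slope.**

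- Non-urological patients: 13,720 × 5/6 = 11,433. At 5% SSI the information is 0.0871 per patient, z = 0.1024 × √(11,433 × 0.0871) = 3.23, power Φ(3.23 − 1.96) = 90%. At 10% SSI the information is 0.166, z = 4.46, power 99%.
- Urological patients: 13,720/6 = 2,287. Power is 51%, 76% and 90% for bacteriuria of 10%, 20% and 35%.

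**The case against.** The substitution is declared openly in the outcome sentence. It also has a reason: the superficial and deep SSI definitions in Appendix A require an incision, which transurethral resection does not provide. Effects may differ just as much between caesarean section, colorectal resection and arthroplasty, which are also pooled. Section 9 speaks of associations in the plural and promises a pre-specified analysis plan, where interaction terms and procedure-specific estimates commonly belong. That plan is not shown and may contain them, so their absence from the Protocol is not itself an error.

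Most of this stands. It does not remove the mismatch within the Protocol. The other pooled procedures share the name SSI; here the event itself changes, and sections 7.2 and 9 drop the change. A later analysis plan can add component results, but the primary outcome and its label are fixed here.

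Two stronger readings are tempting and are not supported:

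- A reader might infer that a null SSI effect would almost always come out significant at about the planned size. That needs a bacteriuria OR near 0.80, about twice the planned log-odds slope (ln 0.80 = −0.223 against −0.102). The documents offer no source for it.
- A reader might set the 10% planning risk against the 5% in section 6.1 and infer that urology must supply most events: (0.10 − 5/6 × 0.05)/0.10 = 58% at a 1/6 share. But 5% describes all NHS surgery, not these procedures. If SSI in the non-urological procedures is 10%, nothing forces bacteriuria to be high.

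**Conclusion.** The point holds as a mismatch between the defined outcome and what the objective and analysis say is being tested. A pooled dose coefficient cannot be attributed to SSI, whether or not procedure is adjusted for. This follows from the text and needs no assumed input.

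The size does need assumed inputs. Across the ranges above, a bacteriuria effect at the planned slope makes the pooled result significant in about 8% to 62% of studies when SSI has no association with dose, against a nominal 5%. Only the stronger assumed effect of 0.80 takes this to about 81% to 99.7%. In the other direction, power falls to about 63% to 70% if SSI risk is 5% and bacteriuria is 20% to 35%, against about 90% in the non-urological patients alone; at 10% SSI the dilution matters little.

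This should be fixed as a cheap improvement. It does not invalidate the study, and it changes neither data collection nor sample size.

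**What to change.** - In sections 7.2 and 9, name the endpoint as section 7.3 defines it.
- In section 7.3, state whether the urinary tract infection or bacteriuria component applies only to urological surgery, so that the sentence and the list agree.
- Include procedure group and a dose-by-urological-surgery term in the primary model.
- Report the dose association for SSI in the non-urological procedures and for bacteriuria in transurethral resection as separate estimates.
- State that the SSI conclusion and the 5% primary test rest on the non-urological estimate, with the urological estimate supportive. This also settles how the 5% is used across the two.

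The cost is wording in the Protocol and the analysis plan, with no new data. The downside is precision. At a 1/6 share and OR 0.903, the urological estimate has power of about 51% to 90% for bacteriuria of 10% to 35%, and less if the share is smaller. The SSI estimate uses fewer patients, with power of about 90% at 5% SSI and 99% at 10%. The change should be made before the analysis, because a split introduced afterwards would be post hoc.
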